NIMH	National Institutes of Mental Health
PI	Principal Investigator
PLWH	People Living With HIV
PST	Problem Solving Therapy
SA	South Africa
SAMRC	South African Medical Research Council
SDS	Social Distance Scale
sIMB-CIM	Situated Information Motivation Behavioral Skills Model of Care Initiation and Maintenance
SSA	Sub-Saharan Africa
SU	Substance Use
TAU	Treatment As Usual
TB	Tuberculosis
UMD	University of Maryland
US	United States

1. OVERALL AIM AND SPECIFIC OBJECTIVES

1.1 Overall Aim

The overall aim of this study is to test the feasibility, acceptability, fidelity, and preliminary effectiveness of a community health worker (CHW) training programme. The goal of this program is to reduce stigma on the part of CHWs towards patients living with HIV/tuberculosis (TB) and with depression or substance use (SU) in order to better help these patients re-engage in TB/HIV care. The training we propose to test was informed by formative interviews conducted with CHWs, other stakeholders, and patients in South African Medical Research Council (SAMRC) Protocol #EC039-9/2020.

We wish to extend our initial feasibility test of the training into a larger, stepped-wedge pilot trial. Findings will inform future iterations of this training at a larger scale.

1.2 Specific Objectives

1.2.1. Initial Pilot Training

To test the feasibility, acceptability, and fidelity of this CHW training program, we will:

- a. Train CHWs in the adapted training program ($n = 25$)
- b. Conduct assessments with the CHWs ($n = 25$) to obtain feedback on the perceived appropriateness, acceptability, and feasibility of the adapted training. We will also assess a representative sample of patients seen by the CHWs following the training ($n = 75$). Patients will be asked about the presence or absence of stigmatizing behaviours from each of the CHWs.
- c. Code a subset of audiotaped CHW visits and/or behavioural role plays ($n=25$) to assess fidelity to the training
- d. Adapt the implementation strategy and content (if needed) of the CHW training program based on findings from objectives b and c.

1.2.2 Stepped-Wedge Pilot Trial

To further evaluate the implementation (feasibility, acceptability, fidelity) and preliminary effectiveness of this CHW training program to reduce CHW stigma towards depression and SU in order to promote re-engagement in TB/HIV care, we will conduct a Type 2, hybrid effectiveness-implementation trial.¹ This will be guided by Proctor's implementation model.² Using a stepped-wedge design with multiple NGO/clinic sites ($N = 60$ CHWs total), we will randomly allocate the timing of the CHW training (versus treatment as usual; TAU) over six months. The following multi-level outcomes will be evaluated:

- a. Feasibility, acceptability and fidelity of the CHW training (primary implementation outcomes). This will be assessed through both quantitative and qualitative methods so that qualitative data can add key context to quantitative findings and will include both CHWs and stakeholders (e.g., NGO leaders, policymakers focused on CHW training, supervisors of CHWs) to identify potential organizational barriers and facilitators to implementation of the training beyond the course of this study.
- b. CHW stigma towards depression and SU in TB/HIV patients (primary; effectiveness outcome)
- c. Patient re-engagement in TB/HIV care over six months via chart review (secondary effectiveness outcome)

2. INTRODUCTION

2.1 Background and Rationale

Globally, South Africa (SA) is in the top three countries with the highest burdens of HIV and TB.³ With approximately 7.7 million people living with HIV (PLWH), SA has the most HIV cases in the world,^{3,4} and PLWH are over 20 times more likely to develop TB than HIV-uninfected individuals.⁵ TB is a leading cause of death in SA, and PLWH have the highest burden of TB.⁶

Poor engagement in care contributes to HIV and TB morbidity and mortality in SA, and depression and SU contribute to poor engagement in TB/HIV care. In SA, 62% of PLWH are on HIV medication³ – called antiretroviral therapy (ART) – and over 70% of individuals with TB are diagnosed and initiated on treatment.⁷ However, nearly half of PLWH have not achieved viral suppression,³ and only about half of people with TB successfully complete treatment (29% are LTFU between TB diagnosis and treatment completion).⁷ Individuals with depression and/or SU are particularly susceptible to poor engagement in TB/HIV care, including missed visits and greater likelihood as being LTFU.^{8,9} Approximately one-third of PLWH have hazardous alcohol use,¹⁰ over half have elevated depressive symptoms,^{9,11} and rates are even higher among TB/HIV co-infected patients.^{8,12} In previous studies, our team has shown a 42% lower odds of HIV treatment adherence among PLWH with depressive symptoms versus those without elevated depressive symptoms, and that depressive symptoms are associated with poorer engagement in HIV care.⁹ Further, our team has also shown that alcohol use is associated with 2 times greater odds of poor TB outcomes, including treatment failure and LTFU, and poor HIV adherence.^{13,14}

CHWs are frontline workers in SA who play a central role in re-engaging patients who are LTFU in TB/HIV care. As part of SA's national strategy for HIV and TB care,¹⁵ CHWs are deployed in communities to provide active support for patients, including finding PLWH and TB-infected individuals who have been LTFU. Community-based, CHW-delivered interventions show promising outcomes, including improved engagement in care and treatment completion for patients with TB/HIV co-infection.^{16–19} However, barriers continue to remain for TB/HIV re-engagement.

CHWs need additional support and training to manage patients with depression and/or SU in TB/HIV care. Despite the prevalence of depression and SU in TB/HIV co-infected individuals⁸ and the impact on engagement in care, CHWs receive little, if any, training on how to respond and re-engage people with depression and/or SU in care. In fact, although CHWs form an integral part of SA's response to the HIV epidemic, CHW training programs in SA do not routinely provide training in mental health (MH) comorbidities such as depression or SU. In our team's pilot data with CHWs in SA ($n=66$), 63% reported not having prior training on depression or SU, although over 90% were 'very interested' in learning how to support these clients.²⁰

High levels of MH and SU stigma exist among CHWs, which is a central barrier to patient re-engagement in care. Our team's pilot data also demonstrated high levels of stigma towards SU and depression among CHWs ($n=66$). Using the Social Distance Scale (SDS), 79% of CHWs had moderate to high stigma towards patients with SU, and 53% had moderate to high stigma towards patients with depression.²⁰ These findings are aligned with other research on stigma and CHWs in sub-Saharan Africa (SSA).²¹ Additionally, our team has found extensive qualitative evidence that CHW SU stigma is a major barrier to care engagement, with patients describing feeling "scolded", "judged" and disrespected for SU,^{22–24} resulting in reluctance to both access

and continue HIV and TB care.²⁵ Other work by our team has also shown that PLWH with depression and/or SU²⁶ report lack of respect and stigma from CHWs as a barrier to accessing care.²⁷ There is also quantitative evidence that PLWH experience high levels of stigma related to MH – and particularly to SU – that contributes to delays in seeking or re-starting care.²⁸ Further, there is evidence that when CHWs have negative attitudes towards patients with depression or SU, they spend less time with these patients, are less likely to implement evidence-based practices, and deliver less patient-centred care.²⁹ At the same time, it is well documented that MH and SU stigma lead to negative health outcomes among patients including patient delays in seeking treatment, lower treatment continuation rates, and poorer physical health.^{30–32} In SA specifically, patients have been found to stop seeking TB/HIV care or terminate prematurely due to stigmatisation of MH-related symptoms.³³ Yet, to date, few studies have explored how to reduce CHW stigma as a means to improve re-engagement in TB/HIV care.

There is evidence that MH-related stigma reduction interventions in low and middle-income countries (LMICs) can reduce discrimination and improve patient outcomes. In SSA, stigma reduction strategies for TB and HIV stigma have demonstrated efficacy for reducing discriminatory practices among health workers and improve patient-level outcomes, including engagement in TB and HIV care.^{34–37} However, compared to TB- and HIV-related stigma, there is much less research on how to shift MH and SU-related stigma in LMICs, particularly in the context of TB/HIV care. The limited evidence available indicates that the most effective MH-related stigma reduction interventions among healthcare workers include social contact with peers or service users.^{36,38} However, this research is still in early phases^{36,38} with the impact of these interventions on patient-level care outcomes rarely examined.³⁶

The proposed training integrates two conceptual models: the Link and Phelan stigma framework³⁹ and the Situated Information Motivation Behavioural Skills Model of Care Initiation and Maintenance (sIMB-CIM).⁴⁰ According to the Link and Phelan stigma framework, stigma may occur among providers (including lay health workers, such as CHWs) when (1) individuals label differences and attach negative stereotypes to others and (2) the 'us' and 'them' are separated leading to status loss, discrimination, and conditional access to care. The sIMB-CIM model guides the identification of relevant contextual variables that may affect patients' re-engagement in care and suggests that engagement and maintenance in care is determined by (1) accurate information about one's illness; (2) intrapersonal and interpersonal motivation; and (3) behavioural skills, including systems navigation and organizational/planning skills, all of which may be affected by depression and SU.

Guided by the conceptual models, our proposed CHW training integrates two-evidence based CHW training approaches that have not previously been integrated with information from qualitative interviews in SAMRC Protocol #EC039-9/2020. The proposed training integrates:

- (1) a CHW-training developed in SA⁴¹ to increase awareness and understanding of depression and SU and reduce stigma—which addresses the *Information* element of sIMB-CIM; and
- (2) evidence-based skills for promoting re-engagement in care (i.e., problem solving therapy; PST) and motivational interviewing (MI), previously adapted for CHW delivery in SA⁴²—which addresses the *Motivation* and *Behaviour* elements of sIMB-CIM.

2.2 Adapting Training for the Initial Pilot Trial

We previously conducted a rapid analysis of Phase 1 interviews (#EC039-9/2020) to guide adaptations to the training in three domains: (1) training content; (2) training structure; and (3) the implementation strategy. Through this, we identified the need for ongoing supervision, monitoring, and consultation with CHWs; the need to consider how to incorporate cultural beliefs and

practices into the training; and the need to consider how to incorporate lived experience into the training to reduce stigma.

Based on these qualitative interviews, we determined that:

- The training should be at least three days long
- The training should cover basic information about depression and substance use along with information about stigma
- The training should focus on empowering CHWs to work with patients who have depression or are struggling with SU, as currently many CHWs feel underprepared to help such patients.

2.3 Adapting Training for the Stepped-Wedge Pilot Trial

Based on the findings of the initial training, we will adapt the training for a larger pilot test. We will use a randomized, hybrid Type 2 effectiveness-implementation design¹ to compare the adapted CHW training to usual CHW training (treatment as usual; TAU) in this setting. This type of design builds evidence for the effectiveness of an intervention in a real-world context, while also supporting the transition to implementation for subsequent, larger trials, with an equal emphasis on effectiveness and implementation.

This hybrid Type 2 effectiveness-implementation study will utilize a stepped wedge design to maximize power and ethically ensure that all clinics receive the CHW training, while also including a rigorous comparison condition. In this pilot trial, all clinics will receive the CHW training; each clinic will be randomized to the timing in which their CHWs receive the training.

Before CHWs receive this adapted training, they will receive TAU. In TAU, a CHW is typically deployed to a patient's home who has TB/HIV and has been LTFU for TB and/or HIV treatment with the central goal for supporting re-engagement in TB/HIV care. The CHW Typically goes to the patient's home twice per week for one month, or until the patient has re-engaged in care (if less than one month). CHWs typically meet with supervisors weekly for monitoring, which is limited to target review and does not include additional skills training or psychosocial debriefing. CHWs typically routinely document their visits to facilitate supervision and monitoring, and as part of efforts to roll out screening for depression and SU.

3. RESEARCH WORK PLAN

Aims: The aims of this study are to test the implementation (feasibility, acceptability, fidelity) and preliminary effectiveness of a CHW training programme. The goal of this program is to reduce stigma on the part of CHWs towards patients living with TB/HIV and with depression or substance use (SU) in order to better help these patients re-engage in TB/HIV care. We have adapted this training first based on interviews with patients and stakeholders in SAMRC Protocol #EC039-9/2020.

We are initially piloting this training with a small group (up to $n=25$) CHWs. Based on the feedback from these CHWs and our study team running the training, we are making small adaptations to the training. We will pilot this updated training with a larger group of CHWs ($n=60$) using a stepped-wedge design.

3.1.2 Stepped-Wedge Trial of the Training

We will recruit CHWs employed by our partner NGOs (see above) who work at one of the clinics this study has partnered with. The exact clinics will be determined based on ongoing conversations with the Western Cape Department of Health, the City of Cape Town, and the NGO's. We expect the majority of clinics – if not all – to be based in Khayelitsha.

3.2 Study Design

3.2.1 Initial Training

We will invite up to 25 CHWs to participate in a pilot training. As the purpose of this activity is to gather feedback from the CHWs about their experiences with the brief training—rather than to test the effectiveness of the training—all enrolled CHWs will receive the training.

3.2.2 Stepped-Wedge Trial

We will use a stepped-wedge design.

CHWs will be clustered based on the site at which they work. When recruiting participants, we will aim to recruit approximately 20 CHWs per cluster.

CHWs across all clusters will be recruited and complete a baseline assessment at approximately the same time. In stepped-wedge trials, all groups have different intervals of a baseline period in which they are not exposed to an intervention (which we refer to as “treatment as usual” or “TAU”). Following this, at measurable intervals (steps), one group at a time will receive the training intervention. This process continues until all clusters have received the intervention. Then, at least one more follow-up assessment occurs after all clusters have received the intervention.

In this study, when a cluster receives the intervention (versus continues TAU) depends on whether they are randomized to Training Time #1, Training Time #2, or Training Time #3. Each training time will occur at a measurable intervention (compared to when the baseline assessment was conducted) so that the doses of TAU are discernable.

During data analysis, outcome variables will be compared between people before taking the intervention (TAU only; timepoints are baseline assessment (t1) and pre-training assessment (t2)) and with the same group of people after the intervention (TAU+Training; additional timepoints are 3-month follow-up (t3) and 6-month follow-up (t4) after adjusting for individual random effect and time effect.

Randomization will not affect any other TB/HIV-related clinic services or mental health training.

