3.5.2 Stepped Wedge Trial

3.5.2a CHW Screening & Consent

Potentially eligible CHWs—referred to us by NGO staff will be screened for eligibility. If eligible and interested in participating, they will undergo informed consent procedures. As part of this process, participants will be informed of all the potential risks and benefits to taking part in the study. Participants will be reminded that participation is voluntary, that they can decline to answer any questions they are not comfortable answering, they can leave the study at any point, and their decision to participate in the study will not impact their job. As part of signing the consent form, they will also consent to the Protection of Personal Information Act 4 of 2013.

3.5.2b CHW Baseline and Pre-Training Assessments

Baseline Assessment. Upon giving willing, informed consent, CHWs will complete a baseline assessment with study staff. The baseline assessment will consist of self-report questions around CHWs' demographic characteristics and job, personal mental health questions, questions around knowledge of HIV, TB, depression and substance use, and questions around stigma.

Pre-Treatment Assessment. Immediately before their training, participants will complete a pre-training assessment. At this visit, participants will be asked to answer the same self-report questionnaires and as they did at baseline (with the exception of demographic and job information, which will not be asked again). All CHWs will also complete a brief (~10 minutes) role-play vignette with a staff member who is minimally involved in delivering the training, which will be videotaped and later coded for stigma using the ENACT.

3.5.2c CHW Training

After the baseline assessment all groups will receive at least one dose of TAU. Based on the training time to which their cluster was randomized, CHWs will then be invited to participate in a training on mental health and substance use.

Clusters randomized to Training Time #1 will receive the training first (while the other training times continue to receive TAU), followed by Training Time #2 (while the final training time continues to receive TAU), and finally, Training Time #3.

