The training in the stepped-wedge trial will be the as the initial training, with minimal adaptations based on participant feedback (e.g., potentially an additional day, allocating more or less time to specific concepts, etc.). It will still be conducted in English, as all CHW trainings offered by the Western Cape Department of Health are required as part of the CHW certification occur in English. Roleplays will be conducted in English (training language) or isiXhosa (patients' language). Additionally, our training team consists of English, isiXhosa, and Afrikaans mother-tongue speakers; therefore, our team will be able to address questions and further explain concepts in these languages if needed.

3.5.2d CHW Post-Training Assessments

In addition to the Baseline and Pre-Treatment Assessments (which both occur before the training, and therefore, measure TAU), CHWs will also be required to complete two additional assessments after the training:

3-Month Follow-Up Assessment (3MFU): All participants will be invited to complete a follow-up assessment approximately 3-months after their training (3MFU). At this visit, participants will answer the same self-report questions they answered at the Pre-Training Assessment, answer additional questions about their perceived feasibility/acceptability of the training, and complete a roleplay for later ENACT coding.

6-Month Follow-Up Assessment (6MFU): All participants will also be invited to complete another follow-up assessment approximately 6-months after their training (6MFU). At this visit, participants will answer the same self-report questions they answered at the 3MFU and complete a roleplay for later ENACT coding. A subset of CHWs will also participate in semi-structured individual interviews in which they answer open-ended questions about their perceived feasibility/acceptability of the training.

3.5.2e Additional CHW Self-Report Measures

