CHWs will complete the same measures during the stepped-wedge trial as they did in the initial training. In addition, they will also complete an integrated measure that assesses stigmas related to HIV and TB, which has been previously validated among health workers in South Africa.^{49,50} Additionally, the personal questions around personal mental health/ substance use will be slightly expanded upon (i.e., asking about self and friends in addition to family). Although there is not an immediate post-training assessment, participants will additionally do another roleplay on their last day of training, which will be rated using the ENACT.^{45,46} Please see Initial Training Procedures (above) for more information on the roleplay.

Based on feedback from the initial training, measures used in the initial training may also be shortened or slightly reframed (e.g., only asking the feasibility and acceptability subscales of the D&I measure).

3.5.2f Stakeholder Screening and Consent

Potentially eligible NGO leaders and stakeholders will be screened for eligibility. If eligible and interested in participating, they will undergo informed consent procedures. As part of this process, participants will be informed of all the potential risks and benefits to taking part in the study. Participants will be reminded that participation is voluntary, that they can decline to answer any questions they are not comfortable answering, they can leave the study at any point, and their decision to participate in the study will not impact their job. As part of signing the consent form, they will also consent to the Protection of Personal Information Act 4 of 2013.

3.5.2g Additional Measurements

Training Feasibility. CHW attendance in the training (less than one-week) and will be assessed as one measure of training feasibility. Over 75% of training sessions attending across all CHWs will be used as a benchmark for assessing whether the training is feasible.²

CHW Fidelity. To assess the fidelity of CHW delivery of training components (e.g., using non-judgmental communication, implementing MI/PST skills), 20% of the 3MFU roleplays will be randomly selected and rated using a fidelity assessment rating form in addition to being rated on the ENACT. A fidelity score will be calculated based on the proportion of key intervention components delivered as intended across the interactions based on these ratings.

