4.3 Primary Preliminary Effectiveness Outcomes (Stepped-Wedge Trial Only)

4.3.1 –Stepped Wedge Trial

CHW Stigma. The primary measure of CHW stigma is the Social Distance Scale (SDS),^{20,43,44} a well-validated measure of stigma used to capture health-related stigma across conditions and has been recommended for assessing mental health stigma among healthcare providers. A total SDS score will be calculated to represent CHW stigma towards the target population at each timepoint, with high scores indicating greater desire for social distance. First, we will conduct descriptive analyses (e.g., mean, standard deviation) to summarize the CHW stigma, using the continuous SDS score. The data distribution will be assessed to see whether the underlying assumptions are met (e.g., normality). To account for the stepped wedge study design, we will fit a linear mixed model (LMM). This analytic approach will allow us to account for both random effects of the clinic and CHW, and fixed effects of time and the effect of the training. We will analyze the within- and between-group effects. Specifically, the within group effect will evaluate changes in stigma before and after receiving the training with CHWs from the same clinic,

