and the between group effect will compare the CHW training to assessments before the CHW training. An F-test will be used to test the between and within clinic intervention effects. Covariates (i.e, CHW demographic and job-related characteristics) will be included in the model. The model accounts for any baseline differences in CHW stigma between clinics and individual CHWs. Secondary measures of CHW stigma will include behavioral coding to stigmatizing responses in a role play based on vignettes using the ENACT scale.^{45,46,51} Specifically, we will examine whether specific ENACT items (interpersonal skills sub-scale) at the pre-training timepoint predict other ENACT items (clinical skills sub-scale) at the later timepoints using multivariate linear models. This will allow us to begin to explore whether pre-training ENACT roleplays could be helpful for pre-training screening of CHWs in future research. We will also examine improvement in individual ENACT items across the data collection timepoints to examine the effect of the training and supervision on CHW helping skills and the durability of CHW helping skills over time. Additionally, analyses will be conducted on the an integrated HIV and TB stigma scale to measure intersectional HIV and TB stigmas. This scale has previously been validated among health workers in SA.^{49,50}

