6.4 Disclosure of any conflict of interest

Each investigator will complete a conflict of interest statement which will be kept on file by the study team. Any new investigators or key study staff will complete these forms, which will be stored and kept on record. At this time, there are no conflicts of interests in this study.

7. Timeline

Initial Training:

Week	Task	Amount of Time
Week 1		
Week 2	Finalize training manual, set training date, and recruit CHWs	1 month
Week 3		
Week 4		
Week 5	Training (including pre-training and post-training assessment)	3 – 5 days
Week 6		
Week 7	Weekly supervision, roleplays, audio-recordings, and patient	
Week 8	consents/ assessments	1-month
Week 9		
Week 10	1-Month Follow-Up Assessment	~30min per CHW

Upon receiving ethics approval for stepped-wedge trial, approximate timeline:

Month	Group 1 ~20 CHWs	Group 2 ~20 CHWs	Group 3 ~20 CHWs
1			
2		Finalize minor adaptions to training manual, work with NGOs and Western Cape Department of Health, recruit CHWs	
3	Baseline Assessment + TAU	Baseline Assessment + TAU	Baseline Assessment + TAU
4	TAU	TAU	TAU
5	Pre-Treatment Assessment + Training + Supervision	TAU	TAU
6	Supervision	Pre-Treatment Assessment + Training + Supervision	TAU
7	Supervision	Supervision	Pre-Treatment Assessment + Training + Supervision
9	3MFU	Supervision	Supervision
10		3MFU	Supervision
11			3MFU
12	6MFU		
13	Stakeholder (CHW and providers) interviews	6MFU	
14		Stakeholder (CHW and providers) interviews	6MFU
15			Stakeholder (CHW and providers) interviews

TAU = treatment as usual

8. Management Details

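### No planned month has the primary stigma score (SDS) measured in both trained and untrained CHWs, so the randomised timing supplies no concurrent control and the stated 86% power does not apply

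*Combined protocol and SAP*

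**What the plan says.** The SDS is the primary effectiveness measure, and N=60 was chosen on its power (3.3.2a).

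- **Visits.** All groups have baseline at about the same time (3.2.2). For the second visit, "Immediately before their training, participants will complete a pre-training assessment" (3.5.2b). The third and fourth come about 3 and 6 months after the group's own training (3.5.2d). No SDS is taken when training ends: "Although there is not an immediate post-training assessment, participants will additionally do another roleplay on their last day of training" (3.5.2e).
- **Dates.** In the Section 7 table the cell "Pre-Treatment Assessment + Training + Supervision" falls in months 5, 6 and 7 for Groups 1, 2 and 3. The 3-month visits are in months 9, 10 and 11, and the 6-month visits in months 12, 13 and 14. The table has no month 8.
- **Comparison.** Section 3.2.2 sets before against after: "timepoints are baseline assessment (t1) and pre-training assessment (t2)) and with the same group of people after the intervention".
- **Model.** Section 4.3.1 specifies a linear mixed model with "random effects of the clinic and CHW, and fixed effects of time and the effect of the training". It does not say whether time is categorical or linear. It adds that "the between group effect will compare the CHW training to assessments before the CHW training".
- **Claims.** Section 2.3 justifies the stepped wedge as maximising power "while also including a rigorous comparison condition". Section 3.3.2a states 86% power at a standardised effect of 0.63 and 96% at 0.75.

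**The concern.** A stepped wedge separates the intervention from calendar time because, at each step, some clusters have crossed over and others have not, and both are measured. Here each group is measured around its own training. A waiting group has its last untrained SDS before any trained group has its first trained one, so randomising the order creates no month with a randomised contrast.

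Two things are at stake. The plan permits a primary effectiveness model that returns no training effect at all. If the form of time avoids that, the estimate rests on an assumed trend, and the power that justified 60 CHWs belongs to a different layout. A reader of 2.3 and of the between-group test in 4.3.1 would take the SDS result as a concurrent comparison, which it is not.

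**Working it through.** **Inputs.** From the plan: 60 CHWs in three groups of about 20; correlations of 0.1 within clinic and 0.3 within person; effects 0.63 and 0.75; significance level 0.05 (3.2.2, 3.3.2a). Assumed: two-sided tests, total variance 1, known variances, no dropout, no clinic-by-period variation. The plan does not say whether 0.3 includes the clinic part, so both readings are run: CHW share 0.3 (residual 0.6) or 0.2 (residual 0.7), each with clinic share 0.1.

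**Method.** Generalised least squares with random intercepts for clinic and CHW. SE is the square root of the training entry of (X′V⁻¹X)⁻¹, and power = Φ(δ/SE − 1.96).

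**1. The plan's own figure.** The stated powers imply SE = 0.63/(1.96 + 1.08) = 0.207 and 0.75/(1.96 + 1.75) = 0.202. A complete stepped wedge (three groups of 20, four periods, every group measured in every period, categorical time, total within-person correlation 0.3) gives SE 0.201 and power 88% and 96%. With 0.3 added on top of 0.1, SE is 0.186 and power 92% and 98%. The stated figures are therefore close to a layout in which every group is measured at every step.

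**2. Overlap in the planned schedule.**

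| Group | Untrained SDS, months | Trained SDS, Section 7 months | Trained SDS, exactly 3 and 6 months after training |
|---|---|---|---|
| 1 | 3, 5 | 9, 12 | 8, 11 |
| 2 | 3, 6 | 10, 13 | 9, 12 |
| 3 | 3, 7 | 11, 14 | 10, 13 |

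The last untrained month is 7; the first trained month is 9 (or 8). No month has both.

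**3. Categorical time.** With visits t1–t4, the training indicator equals the t3 dummy plus the t4 dummy: five columns, rank 4. With calendar month there are ten distinct months, so the columns are an intercept, nine dummies and training: 11 columns, rank 10, because training is the sum of the dummies after month 7. The calendar-month rank is the same under either numbering and with six clinics of 10 (4.1.1 mentions six clinics). This is algebra and depends on no variance assumption.

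**4. Linear month.**

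| Follow-up months | SE | Power at 0.63 (stated 86%) | Power at 0.75 (stated 96%) |
|---|---|---|---|
| 9–14 (Section 7) | 0.247–0.267 | 66–72% | 80–86% |
| 8–13 (exact) | 0.218–0.235 | 76–82% | 89–93% |

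For example, 0.63/0.267 − 1.96 = 0.40 and Φ(0.40) = 66%. Six clinics change these powers by less than one point. To reach 86% at 0.63 would need about 90–102 CHWs (months 9–14) or 72–78 (months 8–13).

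**5. What linear time does and does not remove.** A steady drift of 0.03 SD per month biases the effect by 0.00. A step between month 7 and the first follow-up has the same pattern as the training indicator, so it enters with multiplier 1. The plan gives no figure for secular change, so the following sizes are illustrative. Steps of 0.10, 0.20 and 0.30 SD add 0.10, 0.20 and 0.30 to the coefficient. With no true effect they give 7%, 12–15% and 20–28% rejections. In the other direction, a one-off fall of 0.30 SD at the first retest after baseline hides 0.13–0.18 SD of a real reduction.

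**The case against.** The strongest reply is that the plan largely discloses a before-after comparison. Section 3.2.2 says the same people are compared before and after, and 4.3.1 defines the between-group effect against pre-training assessments. The form of time is not stated, so aliasing is a possibility and not a certainty. If time is elapsed time, the effect is estimable and the randomised stagger of the second visit helps to estimate the pre-training trend.

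The power shortfall also depends on dates. Section 7 is headed as approximate, omits month 8 and puts the 3-month visit four months after the training month. With visits at exactly 3 and 6 months the gap is 4 to 10 points. The step sizes are illustrative. Finally, this is a pilot of preliminary effectiveness whose implementation outcomes are also primary and are untouched.

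Most of these points stand as limits. The conclusion is conditional on the form of time, the larger power gap needs the Section 7 months, and the step sizes show vulnerability, not likely bias. They do not remove the core. Neither reading of the dates creates overlap, and no other SDS assessment fills the gap. Slippage in dates might create overlap by accident, but none is planned. The before-after wording in 3.2.2 does not support the 86% and 96% in 3.3.2a or the claim in 2.3. The pilot label is only partial mitigation, because the sample size was justified by SDS power.

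**Conclusion.** The concern holds and needs correcting. For the SDS, the plan is a before-after comparison without concurrent controls. With categorical time the training effect is not estimable. With linear time it depends on extrapolation, and power at 0.63 is 66–72% (Section 7 months) or 76–82% (exact 3- and 6-month visits) against 86%; at 0.75 it is 80–86% or 89–93% against 96%.

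The overlap and rank results need only the visit schedule. The powers assume two-sided tests, known variances, equal groups, no dropout and no clinic-by-period variation, so they are upper bounds. For example, with three clusters and an assumed cluster autocorrelation of 0.8, linear-month power at 0.63 falls to 47–51% (months 9–14) or 57–61% (months 8–13).

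The conclusion does not extend to the implementation outcomes or to the ENACT roleplay on the last training day.

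**What to change.** **Minimum: wording and a recalculation, no new visits.**

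- In 3.2.2 and 4.3.1, state that the SDS analysis is an uncontrolled before-after comparison, and specify an estimable form of time.
- For the SDS, withdraw the comparison claim in 2.3 and any reading of the between-group test as concurrent.
- Restate the power in 3.3.2a for the actual schedule, after reconciling the Section 7 months with the follow-up intervals in 3.5.2d.
- Report sensitivity of the training effect to a stated range of non-linear secular change.

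**Option: create a concurrent comparison.** Add a short SDS for Groups 1 and 3 in month 6 and for Groups 1 and 2 in month 7, and fit calendar month as categorical.

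- *Gain.* The design matrix then has full rank (11 of 11), with SE 0.204–0.219 and power 82–87% at 0.63 under the assumptions above. With a cluster autocorrelation of 0.9 or 0.8 and three clusters, power is 73–77% or 66–69%, so the option does not guarantee 86%.
- *Limit.* The controlled estimate is of the effect one to two months after training, while supervision continues, and rests only on SDS up to month 7. A separate effect at the 3- and 6-month visits remains inestimable (rank 11 of 12). Those changes should be reported as uncontrolled unless a constant effect is assumed.
- *Cost.* 40 + 40 = 80 questionnaires at new assessment points. Sixty suffice if Group 3's month-6 SDS is dropped, which changes the SE by less than 0.001. CHW assessments by phone are already allowed (5.2.3, COVID-19). The amendment must go to the ethics committee first (6.2.2).

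The option is a design choice; the minimum correction is needed if it is not taken up.
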